3.2 Stopping criteria

We plan to administer multiple exposures to CVS in order to encourage experience-dependent long-term plastic change (Hoffman et al., 2002). We will study patients for a maximum of 16 weeks allowing for up to 8 weeks of stimulation. Our previous studies suggest that a 16 week protocol is likely to be feasible for patients and carers to commit to without becoming overly burdensome.

The trial will be stopped if the study clinicians (Drs [name]/[name]) and the chief investigator ([name]), or the local NHS R&D unit or sponsor, agree that a critical number of AEs have been reported. The trial may also be terminated if participants and their carers fail to comply with the stimulation protocol (2 x stimulation sessions per each day).

4. Study Design

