Every four weeks, participants will be assessed on the core symptoms of interest. Their physiological activity will also be measured using EEG and heart rate variability (HRV), the latter of which can be simply recorded from one of the EEG electrodes. At the end of the treatment protocol the full baseline assessment will be repeated. 4 weeks post-intervention, the full baseline assessment will once again be repeated to assess carryover.

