4.4 Outcome Measures

Responsiveness to CVS will be measured using both behavioural and electrophysiological measures (detailed below). A variety of behavioural measures will be included to capture changes in the diverse array of symptoms patients present with. Physiological measures will also be used to monitor brain activity and more subtle changes in various physical functions and cognitive processes.

Behavioural: PD symptoms will be assessed using a neuropsychological test battery composed of standardised measures designed specifically for PD such as UPDRS and PDQ-39 and questionnaires that probe a variety of processes associated with motor skills and abilities

(inc. 2 Minute Walk, 10 Meter Walk and Timed Up and Go), memory (inc. MoCA); cognition (inc. Mini-Mental State Examination); mood (inc. HADS depression and anxiety); and fatigue/sleep disturbance (inc. Fatigue Severity Scale, Epworth Sleepiness Scale). More generalised benefits and activities of daily living will be assessed using measures such as the EQ5D3L and the Schwab and England Scale.

The behavioural measures will be administered at the two baseline assessments (week 1 and 4) and at the end of the treatment/placebo phases. A sample of the measures will also be administered during the interim monthly assessments and follow-up (weeks 8, 12 and 16).

ERP/EEG analysis: EEG abnormalities in PD are most prominently characterised by slower background activity (Neufeld, et al. 1998; Pin, et al. 1992) and changes of the alpha/theta index (Soikkeeli, et al. 1991). PD is also associated with a reduced and slower P300 response to auditory oddball stimuli. We will record these electrophysiological markers to help identify mechanism of effect and lend a degree of objectivity to the more subjective behavioural assessments. We will also analyse power within the main EEG frequency bands and record heart rate variability during the EEG sessions. EEG/ERP will be recorded at baseline and post-stimulation.

5. Study Participants

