The PD study plans to permit both "in-clinic" and "at-home" use of the device following an initial training session conducted with the patient and their carer under the supervision of the study team. If after the training session the Study coordinator concludes that the subject is ready, the subject will then be allowed to continue twice-daily treatments at home until the end of the treatment period. The patient will be instructed that if she or he has any questions or encounters any issues at home, the patient should immediately call the Study coordinator. If the Study coordinator concludes that the patient is not ready for self-treating at home and that additional training is needed, the patient will be instructed to return to the clinic the next day (when possible) to receive such additional training.

The device contains software features that allow physician control of the patient-specific treatment: controlling application time, temperature, waveform, and number of treatments. Safety lockouts prevent over-use by patients by limiting the prescription and the number of applications per day. Throughout the study, patients are required to complete interim assessments for continued evaluations and monitoring.

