Subjects may be discontinued if they fail to meet the requirements of the protocol or meet one of the withdrawal criteria specified above. Patients are expected to complete two daily sessions of stimulation (an hour apart) and attend regular assessments. If participants fail to meet these expectations the chief investigator will review the patient's records and decide whether termination of their participation is required.

Discontinued subjects will be replaced until the study has met its participant quotient.

9.2C Process of Review

The research team will meet in person if required. We will provide summary tables categorizing and reporting the frequency of AEs. We will also compile and present data on the number, gender and ethnicity of subjects. We will summarize on the number of dropouts from the study, and the reason for withdrawal.

9.2D Committee Report and Compliance with Recommendations

After each meeting, the chairperson of the research team will prepare a summary of their meeting with appropriate recommendations. The report will be distributed amongst the team and the R&D departments of the participating trusts.

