***Caloric Vestibular Stimulation in
Parkinson's Disease***

NCT02703844

July 25, 2018

Statistical Analysis Plan (SAP)

Caloric Vestibular Stimulation to Treat Symptoms Associated with Parkinson's Disease

Prepared by: [name], Senior Statistician,
Centre for Health Service Studies
University of Kent

Final Version: 10 August 2017

Amended: 15 August 2018

Investigator: [name]

Sponsor: [name]

Signatures for approval of SAP

Prepared by Trial Statistician: [name] (University of Kent)

Signature:

Date:

Reviewed and approved by:

Principal Investigator: [name]

Signature:

Date:

1. Research question

Do repeated sessions of caloric vestibular stimulation (CVS) induce durable, potentially clinically meaningful improvements in the persistent and disabling motor and non-motor symptoms of Parkinson's disease?

2. Study design

This is a prospective single-blind randomised parallel group pilot study. The study was designed to recruit a diverse sample of 32 individuals diagnosed with idiopathic Parkinson's disease from community and outpatient settings. Participants will be individually randomised to active and placebo arms.

Diagnosis	Treatment (2 x 20 mins sessions per day for 8 weeks)	Number of patients (N)
Idiopathic	Active stimulation (cohort 1)	16
	Placebo (cohort 2)	16

Randomisation will be conducted using online randomisation software (www.randomiser.org). All participants will be blinded to the treatment being administered.

Prior to the treatment phase of the study, there will be a 4 week baseline phase to measure the rate of natural and spontaneous recovery. Outcome measures will be recorded at week 1 and week 4, and after the beginning of the treatment phase, every 4 weeks until the end of the study.

3. Outcome measures

The primary assessment time will be 12 weeks follow-up and the following outcome measures will be analysed:

- Non-motor symptom scale total score (NMSS)
- MDS-UPDRS 1 (Non-motor aspects of experiences of daily living)
- MDS-UPDRS 2 (Motor aspects of experiences of daily living)
- MDS-UPDRS 3 (Motor Examination)
- MDS-UPDRS 4 (Motor complications)
- MDS-UPDRS total score
- PD-39 total score
- Hospital Anxiety and Depression scale (HADS)
 - Depression total
 - Anxiety total
- Epworth sleepiness scale
- Fatigue severity scale
- Montreal Cognitive exam
- Timed up and go

4. Sample size

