The sample size of 32 participants is based on recommendations by Brown¹ and Lancaster et al² as a minimum sample size required to estimate the variance of outcome measures to inform the design of a subsequent multi-site randomized control effectiveness trial. Based on previous studies, the expected dropout at 12 weeks was estimated as 20% and a total sample of 40 participants is planned to allow for dropout during the treatment and follow-up phase of the study.

5. Description of the dataset used for the analysis

An Excel database of study data will be created by [name]. This will contain a separate sheet for each outcome measure and will include baseline data, participant information (demographic and randomisation details, medical history including time since diagnosis, time on levodopa and use of other medications), outcome measures, treatment and visit dates and compliance data.

Data will be reformatted and imported from the excel database to SAS datasets prior to Statistical Analysis, using the SAS IMPORT procedure.

6. Statistical methods

Composite scores of the individual items of each measure will be calculated. Changes from baseline (average of two baseline measures at week 1 and week 4) will be calculated from the composite scores for statistical analysis.

Outcomes will be analysed using analysis of covariance (ANCOVA) to compare the change in the mean response across treatment groups. The outcomes will be adjusted for baseline by including the baseline measure (average of week 1 and 4) as a covariate.

Diagnostic tests and plots to assess the assumptions of normality will be performed prior to analysis. In the case of non-normality, equivalent non-parametric approaches will be utilised, or where appropriate, the data will be transformed prior to analysis.

The primary analysis will be intention to treat, including all available data for participants enrolled in the study. Non-compliance will be reported as an outcome for each group, and the level of missing data will be reported. Sensitivity analysis may be performed to assess the impact of missing data.

¹ Brown, R. (1995). On the use of a pilot sample for sample size determination. *Stat Med* 14, pp1933-1940.

² Lancaster, G.A. et al. (2004). Design and analysis of pilot studies: recommendations for good practice. *J Eval Clin Practice* 19, pp307-312.

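### Participation can be ended for missed sessions, and nothing secures the week-12 assessment on which the intention-to-treat analysis relies

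*Protocol*

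**What the plan says.** Protocol 9.2B expects two sessions a day and attendance at assessments. If a participant falls short, the chief investigator looks at the records and may "decide whether termination of their participation is required". The object is participation, not device use. The section ends: "Discontinued subjects will be replaced until the study has met its participant quotient".

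The assessments are described for people who follow the schedule. Protocol 4.2 says "At the end of the treatment protocol the full baseline assessment will be repeated", and Annex 1 places that assessment at the final treatment visit. Protocol 4.4 names weeks 8, 12 and 16 for the interim and follow-up assessments. Protocol 9.1 (Home Use) adds: "Throughout the study, patients are required to complete interim assessments for continued evaluations and monitoring". None of these addresses someone whose participation has ended.

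SAP section 3 states: "The primary assessment time will be 12 weeks follow-up". SAP section 6 states: "The primary analysis will be intention to treat, including all available data for participants enrolled in the study". It reports non-compliance by group, leaves a missing-data sensitivity analysis optional, and plans an exploratory analysis in which compliance is a covariate interacting with treatment.

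**The concern.** An intention-to-treat comparison is meant to include people who used the device little. A person with no week-12 score contributes nothing to a week-12 ANCOVA of change, so the analysis can run under its intention-to-treat label while in effect describing those who continued.

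Three things are at stake.

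- **Effect size.** Protocol 3.2 says: "We plan to administer multiple exposures to CVS in order to encourage experience-dependent long-term plastic change". If repeated exposure matters, people who stop early may benefit less. Without them the estimate is too high even when removal is identical in both arms. Protocol 5.2 says the effect sizes from this pilot will power the next trial.
- **Bias with no true effect.** This arises only if removal differs by arm. Only participants are stated to be blinded (Protocol 4.3, SAP section 2). The person deciding on termination is not stated to be blind, so a difference cannot be excluded.
- **Compliance analysis.** The least compliant participants carry the most information on how response relates to compliance. The device log (Protocol section 3) can still show their use; only the outcome is lost.

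**Working it through.** **The plan's own figure.** SAP section 4 wants 32 participants and expects 20% dropout: 32/(1 − 0.20) = 40, as stated. The plan therefore already allows for 40 − 32 = 8 people without week-12 data, or 4 per arm if split evenly. How many would be terminations is not given.

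**Assumptions (not in the documents).** 20 randomised per arm; correlation 0.7 between visits; outcome SD 1 at each visit; 1, 2 or 4 terminated per arm. Four per arm would make every expected dropout a termination, so it is an upper case. Baseline is the mean of weeks 1 and 4, as in the SAP.

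**Standard error.** The baseline mean has variance (1 + 0.7)/2 = 0.85. Residual variance is 1 − 0.7²/0.85 = 0.424, so the residual SD is 0.651. The standard error of the arm difference is 0.651 × √(2/n): 0.21 for n = 19, 0.22 for n = 18 and 0.23 for n = 16.

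**A. No true effect; active-arm losses are the least compliant, placebo losses random.** Let r be the correlation between compliance and week-12 change, assumed 0.2 to 0.5. Approximate bias towards active is r × 0.651 × λ, where λ is the mean of a standard normal after its lowest 5%, 10% or 20% is cut off (0.109, 0.195, 0.350). The last two columns come from simulating the SAP's ANCOVA (20,000 trials per scenario, Monte Carlo error about 0.002 SD).

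| Lost per arm | Formula, r = 0.2 to 0.5 | Simulated | Simulated, half attend week 12 |
|---|---|---|---|
| 1 | 0.014 to 0.035 | 0.011 to 0.030 | not run |
| 2 | 0.025 to 0.063 | 0.022 to 0.057 | 0.011 to 0.027 |
| 4 | 0.046 to 0.114 | 0.043 to 0.107 | 0.022 to 0.049 |

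With the same selection in both arms the bias is at most 0.003 SD in size (2 or 4 lost per arm). If all attend week 12 it is 0.

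Unequal numbers matter more. If those removed do worse by g SD, the bias is g × (fraction removed in active − fraction removed in placebo). For 8 of 40 removed and g from 0.25 to 1.0, a 4/4 split gives 0, a 6/2 split 0.05 to 0.20 SD, and an 8/0 split 0.10 to 0.40 SD.

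**B. Same removal in both arms, with a true effect.** Assume 0.5 SD in those who continue and e = 0 to 0.25 SD in those terminated; f is the fraction terminated. The intention-to-treat effect is (1 − f) × 0.5 + f × e.

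- f = 0.1: 0.450 to 0.475. Ratios are 0.5/0.475 = 1.05 and 0.5/0.450 = 1.11.
- f = 0.2: 0.400 to 0.450. Ratios are 0.5/0.450 = 1.11 and 0.5/0.400 = 1.25.

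Simulation without follow-up gave 0.496 to 0.500. With all 40 observed it was within 0.004 of the intention-to-treat value. Required sample size varies as 1/effect², so an overstatement of 1.11 would make the next trial 1 − 1/1.11² = 19% too small.

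**C. Compliance-response slope.** Treat compliance as normal, pool the arms and lose the lowest 5%, 10% or 20%. The SD of compliance falls to 0.900, 0.844 or 0.764. The standard error ratio is √(40/n kept)/SD: √(40/38)/0.900 = 1.14, √(40/36)/0.844 = 1.25, √(40/32)/0.764 = 1.46. If replacements with the same compliance as those kept restore 40, it is 1/SD = 1.11, 1.19 or 1.31.

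**D. Residual variance.** Simulated understatement (10,000 trials) is 1 to 6% with 2 per arm and 1 to 9% with 4. Sampling error of a variance on 29 degrees of freedom is √(2/29) = 26%, so this is negligible.

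**The case against.** The strongest reply is that this is silence, not contradiction. Section 9.2B forbids no later assessment, termination is discretionary, and the SAP limits itself to available data, plans for 20% dropout and reports missingness. Section 9.2B also refers back to withdrawal criteria that do not appear under that label in the available text. Protocol text between sections 6.2 and 9.1 and a figure in 5.1 could not be read. A provision there cannot be ruled out, and confidence is medium for that reason.

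The size is also open to challenge. Scenario A needs selection that differs by arm, which no passage shows. The 25% in scenario B needs every expected dropout to be a termination without benefit, and even then the excess is 0.10 SD, under half a standard error. Scenario C concerns an exploratory analysis and pools the arms, whereas the SAP plans an interaction. Variance estimation, the SAP's reason for 32 participants, is barely touched. All of this stands.

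Two practical points stand in part. People removed for missing assessments are the least likely to accept an invitation, so full recovery is the optimistic end. The end-of-treatment battery is long, and Protocol 6.1 itself calls EEG burdensome; but EEG is not among the SAP's listed outcomes.

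Timing matters too. The SAP schedules analysis for August to September 2017 and the protocol is dated July 2018, so enrolment may have closed.

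None of this supplies the missing statement. Reporting missing scores does not recover them.

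**Conclusion.** The concern holds. Section 9.2B and the SAP's primary analysis are unreconciled: one can end participation for poor compliance, and no available text keeps the week-12 score that the other would analyse.

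On the stated assumptions the effect is modest. With 2 terminated per arm, bias with no true effect is 0.02 to 0.06 SD if only active-arm losses are selective and about 0 if selection is equal. The overstatement of a real effect is 0.025 to 0.05 SD. With 4 per arm the figures are 0.04 to 0.11 SD and 0.05 to 0.10 SD. The standard error is 0.21 to 0.23 SD. Larger bias needs markedly unequal removal, of which the documents give no sign. The loss of precision for the compliance analysis is proportionately greater: 25% with 2 per arm, or 19% with full replacement.

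This should be fixed because the remedy is cheap and protects an analysis the SAP already promises, not because it threatens the trial.

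**What to change.** In Protocol 9.2B, separate stopping device use from leaving the study. State that participants who stop, or are stopped for missed sessions, are still invited to the week 8, 12 and 16 assessments unless they withdraw from assessment, and are analysed in the arm to which they were randomised.

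As a minor clarification, say whether the recruitment target in the replacement sentence is 32 or 40. Confirm that replacements are randomised as in 4.2 and that those replaced stay in the intention-to-treat set.

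If enrolment has closed, report by arm how many were terminated and how many of those have a week-12 score.

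The cost is one or two sentences and at most three assessments per terminated person: 4 × 3 = 12 visits with 2 per arm, or 8 × 3 = 24 in the upper case. These are already among the 40 × 5 = 200 scheduled (weeks 1, 4, 8, 12 and 16); visits for any replacements beyond 40 would be extra, and some people will decline. No view is taken on when device use should stop.

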9.3 Data Handling and Record Keeping

The primary patient records will be kept as completed questionnaires/reports. When in paper format, these records (de-identified) will be scanned, converted to PDF and uploaded onto a secure web-based system (21 CFR part 11 compliant). Data from the electronic measures will also be stored on this system.

All printed and electronic documentation of enrolled participants will bear the patient's unique ID number (assigned at enrolment) as opposed to their name. A name sheet that connects each trial number to each participant will be kept on a physically separate electronic database.

Printed materials obtained from the various tests and other printed source documentation will be kept in locked filing cabinets in the CI's office. Electronic data collected will be entered, in encrypted format, into a password-protected database by a research team member using a dedicated desktop computer.

An electronic screening log will be kept by the study co-ordinator of all referrals (gender, age, ethnic and racial category), including the number of patients who are initially referred to the study, the number who refuse to be referred, the number who meet eligibility, the number who provide informed consent, and the number who subsequently drop out. The referring physicians will provide information on the number who may meet initial eligibility but refuse to be referred, and the co-ordinator will be responsible for completing all other aspects of the log. No names will be recorded in this log.

All personal data will be handled with extreme care and will adhere to the Data Protection Act and in accordance with MRC guidelines for the handling of personal data.

After final follow-up the Chief Investigator will assume responsibility for maintenance and access to the electronic database and all other data. The Chief Investigator alone will be authorized to make corrections to data and patient records. Researchers will need to contact the Chief Investigator for any data queries or to request an amendment.

Cited Articles

- (1.) Hoehn & Yahr. (1967). Neurology, 17, 427-442.
- (2.) Leentjens et al. (2002). Acta Psychiatrica Scandinavia, 106 (3), 196-201.
- (3.) Lehrner, et al. (2014). European Journal of Neurology, 21:1276-1284.
- (4.) Von Campenhausen, et al. (2005). European Neuropsychopharmacology, 15 (4), 473-490.
- (5.) Kowal, et al. (2013). Movement Disorders, 28 (3), 311-318.
- (6.) Tolosa, et al. (1993). Neurology, 50 (6), S2-S10.

Annex 1: Schedule of Events for idiopathic group

Enrolment/Screening	
 Informed Consent If enrolled, complete Screening Visit form If meet criteria complete participant questionnaire Arrange initial baseline assessment Arrange training session with CVS device
Days 1-4 (up to 4) in patient's home	
 Day 1/ 2- Device training session given to patient and their carer Day 3/4 - Administer full baseline assessment
Day 28: Subject repeats baseline	
 The full baseline assessment is repeated Subject performs a treatment under observation by a research team member to reconfirm proficiency
During the Treatment Period (weeks 4-12)	
 A research team member contacts the patient to ensure that she/he is using the Device consistently and making prompt diary entries A monthly assessment of the core symptoms of interest is completed at the patients' home
Final treatment visit for Subject	
 Complete full baseline assessment Patient returns CVS Device Collect all treatment delivery data from the CVS Device
Follow-up visit for Subject	
 Complete core assessment Debrief patient and carer Interview patient with regard to CVS Device

***Caloric Vestibular Stimulation in
Parkinson's Disease***

NCT02703844

July 25, 2018

Statistical Analysis Plan (SAP)

Caloric Vestibular Stimulation to Treat Symptoms Associated with Parkinson's Disease

Prepared by: [name], Senior Statistician,
Centre for Health Service Studies
University of Kent

Final Version: 10 August 2017

Amended: 15 August 2018

Investigator: [name]

Sponsor: [name]

Signatures for approval of SAP

Prepared by Trial Statistician: [name] (University of Kent)

Signature:

Date:

Reviewed and approved by:

Principal Investigator: [name]

Signature:

Date:

1. Research question

Do repeated sessions of caloric vestibular stimulation (CVS) induce durable, potentially clinically meaningful improvements in the persistent and disabling motor and non-motor symptoms of Parkinson's disease?

2. Study design

This is a prospective single-blind randomised parallel group pilot study. The study was designed to recruit a diverse sample of 32 individuals diagnosed with idiopathic Parkinson's disease from community and outpatient settings. Participants will be individually randomised to active and placebo arms.

Diagnosis	Treatment (2 x 20 mins sessions per day for 8 weeks)	Number of patients (N)
Idiopathic	Active stimulation (cohort 1)	16
	Placebo (cohort 2)	16

Randomisation will be conducted using online randomisation software (www.randomiser.org). All participants will be blinded to the treatment being administered.

Prior to the treatment phase of the study, there will be a 4 week baseline phase to measure the rate of natural and spontaneous recovery. Outcome measures will be recorded at week 1 and week 4, and after the beginning of the treatment phase, every 4 weeks until the end of the study.

3. Outcome measures

The primary assessment time will be 12 weeks follow-up and the following outcome measures will be analysed:

- Non-motor symptom scale total score (NMSS)
- MDS-UPDRS 1 (Non-motor aspects of experiences of daily living)
- MDS-UPDRS 2 (Motor aspects of experiences of daily living)
- MDS-UPDRS 3 (Motor Examination)
- MDS-UPDRS 4 (Motor complications)
- MDS-UPDRS total score
- PD-39 total score
- Hospital Anxiety and Depression scale (HADS)
 - Depression total
 - Anxiety total
- Epworth sleepiness scale
- Fatigue severity scale
- Montreal Cognitive exam
- Timed up and go

4. Sample size

The sample size of 32 participants is based on recommendations by Brown¹ and Lancaster et al² as a minimum sample size required to estimate the variance of outcome measures to inform the design of a subsequent multi-site randomized control effectiveness trial. Based on previous studies, the expected dropout at 12 weeks was estimated as 20% and a total sample of 40 participants is planned to allow for dropout during the treatment and follow-up phase of the study.

5. Description of the dataset used for the analysis

An Excel database of study data will be created by [name]. This will contain a separate sheet for each outcome measure and will include baseline data, participant information (demographic and randomisation details, medical history including time since diagnosis, time on levodopa and use of other medications), outcome measures, treatment and visit dates and compliance data.

Data will be reformatted and imported from the excel database to SAS datasets prior to Statistical Analysis, using the SAS IMPORT procedure.

6. Statistical methods

Composite scores of the individual items of each measure will be calculated. Changes from baseline (average of two baseline measures at week 1 and week 4) will be calculated from the composite scores for statistical analysis.

Outcomes will be analysed using analysis of covariance (ANCOVA) to compare the change in the mean response across treatment groups. The outcomes will be adjusted for baseline by including the baseline measure (average of week 1 and 4) as a covariate.

Diagnostic tests and plots to assess the assumptions of normality will be performed prior to analysis. In the case of non-normality, equivalent non-parametric approaches will be utilised, or where appropriate, the data will be transformed prior to analysis.

The primary analysis will be intention to treat, including all available data for participants enrolled in the study. Non-compliance will be reported as an outcome for each group, and the level of missing data will be reported. Sensitivity analysis may be performed to assess the impact of missing data.

¹ Brown, R. (1995). On the use of a pilot sample for sample size determination. *Stat Med* 14, pp1933-1940.

² Lancaster, G.A. et al. (2004). Design and analysis of pilot studies: recommendations for good practice. *J Eval Clin Practice* 19, pp307-312.

An exploratory covariate analysis of the outcomes NMSS total score, MDS-UPDRS 2 and MDS-UPDRS 3 will be performed to explore the relationship with response and the interaction between treatment group and the covariates age, gender, time since diagnosis, disease severity, compliance, time on levodopa, and other medication use. A sensitivity analysis of these outcomes will be performed excluding participants who have dementia, to reflect the study population of the follow-on study.

Summary statistics of the outcome measures will be calculated and presented in tables. Summary level data will be presented graphically to illustrate the main findings from the statistical analysis. The brief statistical analysis report will include an overview of methods, including details of data transformations and information about missing data, a summary of the main findings from the statistical analysis and summary tables and plots to support these findings.

The data will be analysed using the SAS software package (version 9.2).

7. Planned start and end of analysis

- Start of analysis: 08/2017
- End of analysis: 09/2017
